7.4 Reporting Procedures

Serious Adverse Event reporting will be in accordance with the UCSF IRB Regulations (<http://irb.ucsf.edu/sites/hrpp.ucsf.edu/files/post-approval-reporting-summary-sheet.pdf>) and Code of Federal Regulation Title 21 Volume 5 Part 312.32.

Incidents or events that meet the OHRP criteria for unanticipated problems require the creation and completion of an unanticipated problem report form. OHRP recommends that investigators include the following information when reporting an adverse event, or any other incident, experience, or outcome as an unanticipated problem to the IRB:

- Appropriate identifying information for the research protocol, such as the title, investigator's name, and the IRB project number;
- A detailed description of the adverse event, incident, experience, or outcome;
- An explanation of the basis for determining that the adverse event, incident, experience, or outcome represents an unanticipated problem;
- A description of any changes to the protocol or other corrective actions that have been taken or are proposed in response to the unanticipated problem.

Adverse Event Reporting

SAEs that are unanticipated, serious, and possibly related to the study intervention will be reported to the Independent Safety Monitor(s), UCSF IRB, and NCCIH in accordance with requirements.

- Unexpected fatal or life-threatening AEs related to the intervention will be reported to the NCCIH Program Officer, and Independent Safety Monitor(s) within 3 days of the investigator becoming aware of the event. Other serious and unexpected AEs related to the intervention will be reported within 5 working days.
- Anticipated or unrelated SAEs will be handled in a less urgent manner but will be reported to the Independent Safety Monitor(s), IRB, and other oversight organizations in accordance with their requirements and will be reported to NCCIH on an annual basis.
- All other AEs documented during the course of the trial will be reported to NCCIH on an annual basis by way of inclusion in the annual report and in the annual AE summary which will be provided to NCCIH and to the Independent Monitors. The Independent Safety Monitor(s) Report will state that all AEs have been reviewed.

7.5 Follow-up for Adverse Events

Adverse Events will be followed for outcome information. Study personnel will follow-up with participants on a regular basis (frequency to be determined by the nature of the problem) until the problem has resolved or stabilized. These contacts may be made by the PI or other study physician or personnel (including staff, Project Director) and will be done via phone and/or email or text as the PI deems appropriate depending on the event and situation, and taking into account participant preference as reasonable.

7.6 Safety Monitoring

While the overall risks of this study are low, due to clinical trial design and the use of a treatment that has a low but possible risk of serious adverse effects, we will employ a two-person data safety-monitoring board with outside reviewers. The outside reviewers will not otherwise be part of the study team, and will include an experienced clinical investigators and statistician. The reviewer's CVs will be submitted to NIH, and agreement will be obtained from NIH that the reviewers are suitably qualified before beginning the study. The PI will ensure continuous and close monitoring of participant safety. The PI will report to the DSMB. Study progress and safety will be reviewed weekly by the PI and core study team. A report that will be submitted to the outside reviewer will be compiled every 6 months and will include a list and summarization of adverse events. In addition, the report will address (1) whether adverse event rates are consistent with pre-study assumptions; (2) reason for dropouts from the study; (3) whether all participants met entry criteria; and (4) whether continuation of the study is justified on the basis that additional data are needed to accomplish the stated aims of the study. If the DSMB requires an interim analysis based on the occurrence of severe adverse events, we will develop plans for conducting these in consultation with the statistician on this RCT. The outside monitoring reports will be increased in frequency if two or more Serious Adverse Event's (SAE's) with attribution to study related procedures as possibly, probably or definitely related occur in a six-month period of time. In this situation, SAE's will be reported monthly, and study procedures will be reviewed to determine if changes are needed to reduce the risk of SAEs.

Steps Emanating from Data Review: The DSMB will be able to recommend amendments to the protocol, changes in study procedures, changes to the data collection plan or study forms, or study termination due to safety or other issues. Should recommendations be made to amend the study protocol or terminate the study, these recommendations and planned responses will be forwarded to the NIH program officer within 10 working days. Should the protocol be amended as a result of data review, the UCSF IRB will be notified and the amendment approved prior to study amendment implementation unless the protocol amendment must be implemented to protect the immediate safety of the study subjects. In such a case, the protocol amendment will be immediately implemented and the UCSF IRB will be notified directly after protocol amendment implementation.

The PI will be the primary individual responsible for data and safety monitoring. The DSMB Chair will not be named as a co-investigator on this RCT and will serve as a secondary safety monitor determine what steps should be taken to manage AEs and SAEs if/when they occur. In the event that a SAE is identified, the DSMB Chair will schedule a full meeting of the DSMB and review the results of the SAE report from the UCSF CHR prior to this meeting. The decisions of the IRM and the DSMB will assist [name] with developing plans to implement this RCT in a manner that minimizes research-related risks to participants.

DSMB Reviews. Annual DSMB meetings will be held via teleconference. Where a SAE occurs, a special closed meeting of the DSMB will be convened to determine what changes if any are necessary and if the RCT should be stopped.

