7.3 Adverse Events and Serious Adverse Events

An **adverse event (AE)** is generally defined as any unfavorable and unintended diagnosis, symptom, sign (including an abnormal laboratory finding), syndrome or disease which either occurs during the study, having been absent at baseline, or if present at baseline, appears to worsen. Adverse events are to be recorded regardless of their relationship to the study intervention.

A **serious adverse event (SAE)** is generally defined as any untoward medical occurrence that results in death, is life threatening, requires inpatient hospitalization or prolongation of existing hospitalization, results in persistent or significant disability/incapacity, or is a congenital anomaly.

Laboratory values that will be collected to assess safety: We will monitor serum fasting lipid profiles at baseline, 3, and 6 months (also 12 months in R33 phase). Abnormal lipid values are defined using the Common Terminology Criteria for Adverse Events (CTCAE) v 4.0 criteria provided below (https://evs.nci.nih.gov/ftp1/CTCAE/Archive/CTCAE_4.02_2009-09-15_QuickReference_5x7_Locked.pdf).

Adverse Event: Hypertriglyceridemia

Short Name: Hypertriglyceridemia

MedDRA Code: 10020870

Grade	Description
1	150 mg/dL - 300 mg/dL; 1.71 mmol/L - 3.42mmol/L
2	>300 mg/dL - 500 mg/dL; >3.42 mmol/L- 5.7 mmol/L
3	>500 mg/dL - 1000 mg/dL; >5.7 mmol/L - 11.4 mmol/L
4	>1000 mg/dL; >11.4 mmol/L; life-threatening consequences
5	Death

Adverse Event: Cholesterol high

Short Name: Cholesterol high

MedDRA Code: 10008661

Grade	Description
1	>ULN - 300 mg/dL; >ULN - 7.75 mmol/L
2	>300 - 400 mg/dL; >7.75 - 10.34 mmol/L
3	>400 - 500 mg/dL; >10.34 - 12.92 mmol/L
4	>500 mg/dL; >12.92 mmol/L

AEs to be collected as solicited events at study visits include recent hospitalizations and hypoglycemic episodes. Unsolicited events will be recorded in the study Salesforce database. AE data that is formally assessed at study visits will be compared to existing unsolicited events in participant records to avoid double capture.

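### Cheap safety improvement: the two-event trigger in 7.6 counts only SAEs, and 7.3 does not clearly make related hypoglycaemia that needed help or emergency care without admission an SAE

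*Combined protocol and SAP*

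**What the plan says.** **The trigger.** Section 7.6 sets one numeric rule. Outside monitoring reports "will be increased in frequency if two or more Serious Adverse" Events, with at least a possible link to study procedures, arise in a six-month period. In that case "SAE's will be reported monthly, and study procedures will be reviewed to determine if changes are needed to reduce the risk of SAEs". Short of that, "A report that will be submitted to the outside reviewer will be compiled every 6 months".

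**Other DSMB steps.** Section 7.6 adds: "Where a SAE occurs, a special closed meeting of the DSMB will be convened". Routine meetings are yearly: "Annual DSMB meetings will be held via teleconference". Sections 8 and 9.4 provide closed DSMB review of serious events related to the intervention or assessments. Both also use the word *severe*, which is not defined. Section 7.6 gives the DSMB Chair a wider role, to "determine what steps should be taken to manage AEs and SAEs if/when they occur".

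**The definition.** Section 7.3 describes an SAE, in general terms, as an event that "results in death, is life threatening, requires inpatient hospitalization or prolongation of existing hospitalization", or that causes lasting or significant disability or is a congenital anomaly.

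**Hypoglycaemia.** Section 7.1 identifies it, in people on insulin or sulfonylureas, as a possible serious harm of the diet. Section 7.3 collects it: "AEs to be collected as solicited events at study visits include recent hospitalizations and hypoglycemic episodes". No severity grading is given for these episodes, and no DSMB trigger mentions them.

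**The concern.** The study lowers carbohydrate intake and adjusts glucose-lowering drugs at the same time. The most plausible warning that the reductions are too small is a run of episodes in which a participant needed someone's help, or was treated in an emergency department and sent home. Unless such an episode is judged life threatening or disabling, the 7.3 list does not clearly make it an SAE. Two or three of them in one wave would then not clearly count toward the 7.6 rule, although they are the kind of signal that the rule seems meant to catch.

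What is at stake is how soon people outside the study team look at such a cluster. The frequent reviews belong to the team, including the physicians who apply the medication algorithm. The independent monitors see events below SAE level on a fixed calendar.

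**Working it through.** The plan gives no operating characteristic for the two-event rule, so there is no figure to reproduce. The check sets the provisions side by side and then does calendar arithmetic.

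**Step 1. Does the episode meet 7.3?** Take related hypoglycaemia that needed another person's help or emergency care, with no admission.
- Death, admission or prolonged stay, congenital anomaly: no.
- Life threatening or disabling: only if someone judges it so.
- Any other clause in 7.3 that would include it: none.
- Outside rules cited in 7.4: possibly, but their text is not in the documents and 7.3 does not import it.

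The episode is therefore not clearly an SAE.

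**Step 2. Which reviews does a non-SAE episode reach?**

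| Review | Who | When | Independent? |
|---|---|---|---|
| Glucose values (7.1) | Study physicians | Weekly, first 6 weeks | No |
| Progress and safety (7.6) | PI and core team | Weekly | No |
| AEs and rates (7.2) | PI and internal QA reviewer | Monthly | No |
| Chair's role for AEs and SAEs (7.6) | DSMB Chair | As they occur; no deadline or threshold | Yes |
| AE report (7.2, 7.6) | Independent monitors | Every six months | Yes |
| Annual report and AE summary (7.2, 7.4); DSMB meeting (7.6) | Independent monitors | Yearly | Yes |
| Two-event rule (7.6) | Outside reviewers | Monthly once met | Yes, but counts SAEs only |

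The first scheduled independent look is the six-monthly report.

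**Step 3. How long can that take?** The inputs are the six-month interval (7.6), the 6-week glucose review (7.1), the 12-week course (5.1) and the monthly interval after the trigger (7.6).
- Six months = 365.25 / 2 / 7 = 26.1 weeks. An episode waits between 0 and about 26 weeks for the next report.
- Latest case, with a report compiled just before classes start and the glucose review taken to start with them: 26.1 − 6 = 20.1 weeks after the glucose review ends, and 26.1 − 12 = 14.1 weeks after the course ends.
- One month = 365.25 / 12 / 7 = 4.3 weeks. If these episodes counted, reports would come about every 4 weeks from the second one.
- Largest possible gain for a cluster, if the second episode follows just after a report: 26.1 − 4.3 = 21.8 weeks. The smallest gain is nil, when a report is already due.
- A single episode does not meet the rule and still waits up to about 26 weeks.

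**Step 4. How likely is a cluster?** The documents do not allow an estimate. They give no rate for such episodes, no share of participants on insulin or sulfonylureas and no share of episodes admitted. Section 7.1 expects serious hypoglycaemia to be very rare and reports none in the pilot, which used a similar algorithm. It also puts a 5% ceiling on anticipated risks, though whether that sentence covers hypoglycaemia is arguable.

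**The case against.** The case against is substantial, and most of it stands as a limit on the point.

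- **Correction does not wait for the DSMB.** Section 7.1 requires drugs to be reduced or stopped in a set order when most glucose values fall below 110 or the pattern is worrying. That can act weekly, before any episode. It stands, but it runs for six weeks and is applied by the study team.
- **The DSMB is not confined to SAEs.** The Chair's role in 7.6 covers AEs as they occur, and sections 8 and 9.4 allow closed sessions and a vote on participant-safety issues. So a reader who infers that every DSMB action depends on an SAE goes too far. What remains is that neither provision sets a count or a deadline.
- **The events are seen.** A reader might infer that these episodes go unreviewed. They do not. They are solicited, unsolicited reports are reconciled with them, and the six-monthly report must compare AE rates with what was assumed beforehand. That check needs no contrast between arms, so the fact that both arms share the diet and the algorithm adds nothing to this point.
- **The definition may be wider than it looks.** Section 7.3 offers a general definition and 7.4 cites outside rules. This cannot be settled here, which is why the point says that such episodes are not clearly included, and not that they are excluded.
- **Expedited reporting.** A reader might add that the 3-day and 5-working-day routes in 7.4 would miss these episodes because hypoglycaemia is an expected risk. Admitted hypoglycaemia faces the same test, so this does not bear on the trigger in 7.6.
- **The benefit is unquantified, and the pilot had no episodes.** That is correct. It limits the weight of the point, but 7.1 itself admits uncertainty about adverse-event likelihood with these diets.

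**Conclusion.** The point holds as a low-cost patient-safety improvement, not as an error in the plan. The numeric rule in 7.6 counts only SAEs, and 7.3 does not clearly include non-admitted hypoglycaemia that needed help or emergency care. As a result, no stated trigger or deadline takes a cluster of such episodes to the independent monitors ahead of the six-monthly report.

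The size is a matter of timing only: a wait of 0 to about 26 weeks, against about 4 weeks from the second episode if the rule counted them. This assumes that reports keep to the six-month calendar, that the first monthly report follows within a month, and that the Chair is not alerted sooner under the general role. The 20- and 14-week figures also need a report compiled just before classes start.

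The documents do not support a claim that participants are unprotected, or any stated probability that a cluster would occur or be missed.

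**What to change.** In 7.6, state that a hypoglycaemic episode that needed another person's help or emergency care, and is at least possibly related to the diet or the medication reductions, counts toward the existing two-events-in-six-months rule whether or not the participant was admitted. State also that the resulting monthly reports and procedure review cover these episodes as well as SAEs.

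In 7.3, have the solicited hypoglycaemia item record whether help was needed and whether emergency care was given, and record the same for episodes reported between visits.

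The cost is about two sentences in 7.6 and one or two data items in 7.3. The existing two-person DSMB, threshold and monthly reporting are reused, and decisions on any change stay with the DSMB and study physicians. The downside is that monthly reporting may start more often.

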7. SAFETY ASSESSMENTS

7.1 Specification of Safety Parameters

The key study intervention involves diet changes, which in general is a minimal risk intervention step. The risk of hypoglycemia in persons receiving medications such as insulin or sulfonylureas is a possible serious potential adverse event, however. We anticipate that with the precautions described in detail below, the risk of serious hypoglycemia will be very low. While we encountered no serious adverse events in pilot testing, there has been little careful long-term assessment of adverse events with carbohydrate restricted diets in T2DM, which means there is some uncertainty in predicting the likelihood of adverse events. Other anticipated risks include those associated with venipuncture, psychological testing, and loss of confidentiality. None of these risks are anticipated to occur at a frequency exceeding 5%.

Expected risks to the subject from the carbohydrate-restricted diet are as follows:

1. *Hyperlipidemia:* There have been reports this approach, which involves increases in proportion of calories from fat, causing increases in LDL cholesterol, a risk factor for heart disease. However, several clinical trials of carbohydrate restricted diets for obesity, including three of up to one-year duration, have not shown this relationship:

We will monitor serum fasting lipid profiles at baseline, 3, and 6 months (also 12 months in R33 phase) to assess this potential risk.

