7.2 Methods and Timing for Assessing, Recording, and Analyzing Safety Parameters

Unanticipated problems will be recorded in the Salesforce study database throughout the study. We will record all reportable events with start dates occurring any time after informed consent is obtained until 7 (for non-serious AEs) or 30 days (for SAEs) after the last day of study participation. At each study visit, the investigator will inquire about the occurrence of AE/SAEs since the last visit. We will monitor serum fasting lipid profiles at baseline, 3, and 6 months (also 12 mos in R33 phase). Events will be followed for outcome information until resolution or stabilization.

Safety parameters will be reviewed and analyzed per the schedule below.

Data type	Frequency of review	Reviewer
AEs and rates (including out-of-range lab values)	Monthly	PI, Internal QA Reviewer
	Semi-annually	Independent Monitors
	Annually	NCCIH
SAEs (unexpected and related)	Per occurrence	PI, Independent Monitors, NIH/NCCIH
SAEs (expected or unrelated)	Per Occurrence	PI, Internal QA Reviewer
	Annually	Independent Monitors, NIH/NCCIH
Unanticipated Problems	Monthly	PI, Internal QA Reviewer
	Per Policy	IRB

Study progress and safety will be reviewed monthly (and more frequently if needed). Progress reports, including patient recruitment, retention/attrition, and AEs will be provided to the Monitoring Committee semi-annually. An Annual Report will be compiled and will include a list and summary of AEs. In

addition, the Annual Report will address (1) whether AE rates are consistent with pre-study assumptions; (2) reason for dropouts from the study; (3) whether all participants met entry criteria; (4) whether continuation of the study is justified on the basis that additional data are needed to accomplish the stated aims of the study; and (5) conditions whereby the study might be terminated prematurely. The Annual Report will be sent to the Independent Monitor and will be forwarded to the IRB and NCCIH. The IRB and other applicable recipients will review progress of this study on an annual basis

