9.4 Interim Analyses and Stopping Rules

No interim analyses will be performed and we do not anticipate stopping the RCT early. The primary clinical outcome variable, HbA1c, is a surrogate marker for long-term risk of clinical events in diabetes, but is not an outcome that would justify early termination rules for a study of this size and duration. However, the occurrence of any serious adverse events related to intervention or assessment procedures will be reviewed at length by the DSMB in separately scheduled, closed meetings (if or when severe adverse events occur) to determine whether the RCT should be stopped or enrollment suspended. Where the DSMB considers issues related to participant safety, the DSMB Chair will moderate closed sessions and take a formal vote from DSMB members as to whether the trial should continue given the occurrence of the adverse event(s).

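### SAE routing is inconsistent: section 7.2 sends related but expected SAEs to the independent monitors only annually, while sections 7.6, 8 and 9.4 require a DSMB meeting on them

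*Combined protocol and SAP*

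**What the plan says.** The combined protocol and SAP routes SAEs in five places.

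- **Section 7.2, review table.** SAEs that are unexpected and related go at occurrence to the PI, the Independent Monitors and NIH/NCCIH. The row beginning "SAEs (expected or unrelated" goes at occurrence to the PI and the Internal QA Reviewer only, and annually to the Independent Monitors and NIH/NCCIH.
- **Section 7.4.** The 3-day and 5-working-day limits apply to unexpected related events. For the rest: "Anticipated or unrelated SAEs will be handled in a less urgent manner". They reach the monitors and the IRB according to those bodies' own requirements, and NCCIH annually.
- **Section 7.6, meetings.** Two statements carry no qualifier on relatedness or expectedness: "In the event that a SAE is identified, the DSMB Chair will schedule a full meeting" and "Where a SAE occurs, a special closed meeting of the DSMB will be convened".
- **Section 7.6, reporting.** A report listing adverse events goes to the outside reviewer every 6 months. An escalation rule follows: "The outside monitoring reports will be increased in frequency if two or more" SAEs at least possibly related to study procedures occur within six months. Reporting then becomes monthly.
- **Sections 8 and 9.4.** Both state that "any serious adverse events related to intervention or assessment procedures will be reviewed at length by the DSMB", in separately scheduled closed meetings, to decide whether the study should stop. Neither mentions expectedness.

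Section 7.1 says that hypoglycaemia in people on drugs such as insulin or sulfonylureas "is a possible serious potential adverse event", and places hypoglycaemia second in its list of risks expected from the diet.

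**The concern.** The rules that convene the board and the table that informs it use different criteria. A board can meet on an event only once it knows of it. Section 7.6 gives the DSMB Chair the duty of scheduling the meeting, yet for an expected SAE the section 7.2 table gives the monitors nothing at the time of the event.

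This matters because sections 8 and 9.4 plan no interim analysis. DSMB review of SAEs is the one SAE-triggered process the plan describes for deciding whether to continue. Hypoglycaemia, which section 7.1 itself singles out as possibly serious, is the event most easily caught between the two sets of rules.

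**Working it through.** No arithmetic beyond comparing intervals applies, and the plan gives no figure to reproduce. The check takes each class of SAE through each routing rule.

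| SAE class | 7.2 table: to monitors | 7.4: to monitors | 7.6: DSMB meeting | 8 and 9.4: DSMB meeting |
|---|---|---|---|---|
| Unexpected, related | At occurrence | 3 days if fatal or life-threatening; otherwise 5 working days | Yes | Yes |
| Expected, related | Annually | Less urgent, no interval given | Yes | Yes |
| Unexpected, unrelated | Annually | Less urgent, no interval given | Yes | No trigger stated |
| Expected, unrelated | Annually | Less urgent, no interval given | Yes | No trigger stated |

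**Step 1: three triggers.** Prompt notice needs unexpected *and* related (7.2, 7.4). A meeting needs any SAE (7.6) or any related SAE (8, 9.4). The rules agree only in the first row; the other three of the four classes conflict somewhere.

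**Step 2: expected, related.** Both meeting rules apply, but the table supplies no notice at occurrence.

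**Step 3: unrelated.** Section 7.6 requires a meeting, sections 8 and 9.4 do not call for one, and the table reports annually. This conflict is separate from Step 2.

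**Step 4: where a related serious hypoglycaemia falls.** It is listed among the expected risks in section 7.1, and the plan has no other definition of expectedness. It can therefore be placed in the second row.

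**Step 5: how late the monitors would learn of it.**
- SAE row of the 7.2 table alone: up to 12 months.
- Semi-annual adverse event review (7.2) and six-monthly report (7.6), if SAEs appear in those lists: up to about 6 months.
- Unexpected related SAE, for comparison: 3 days or 5 working days.

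The practical gap is therefore up to about 6 months against days. The six-monthly reports are periodic summaries. They are not per-event notices, and nothing says that they convene a meeting.

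**The case against.** The best defence is that the table is only one of several provisions. Section 7.6 (twice) and sections 8 and 9.4 all convene the board for a related serious hypoglycaemia, so a careful team could follow those and inform the board at once. Such an event might also be judged unexpected in severity: section 7.1 anticipates a very low risk of serious hypoglycaemia and reports no episodes in the pilot. It would then take the fast route. Both points stand as possible readings. Neither removes the conflict, because the plan does not say which provision governs or how expectedness is judged.

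A reader might also infer four stronger things that the documents do not support.

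- *The monitors would wait a full year.* That is the interval in one table row. The semi-annual review and six-monthly report probably shorten it to about 6 months.
- *The escalation rule for two related SAEs in six months would fail.* The rule increases the reports sent to the monitors; it does not depend on the monitors doing the counting. The PI receives every SAE at occurrence, and section 7.6 has the PI and core team review safety weekly, so the study side can apply it.
- *The DSMB is the only way to stop the trial.* Section 11.4 lets the IRB, NCCIH, OHRP and other government agencies discontinue it.
- *Section 7.4 also sets annual reporting to the monitors.* Its annual interval is for NCCIH; for the monitors it sets none.

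**Conclusion.** The inconsistency is real and should be corrected. If staff follow the 7.2 row, a related SAE classed as expected is not sent at occurrence to the board that sections 7.6, 8 and 9.4 require to meet on it. The likely size is a delay of up to about 6 months, against 3 days or 5 working days for unexpected related SAEs. The result is late independent review, with prompt action resting on the PI in the meantime. It is not a loss of oversight.

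Three assumptions underlie this.

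- The six-monthly adverse event lists include SAEs; nothing in the documents excludes them.
- A serious hypoglycaemia can be classed as expected. This rests on the section 7.1 list, so it is a possibility and not a certainty.
- The Independent Monitors, the outside reviewers and the DSMB are the same body, which fits the two-person board in section 7.6. If they are separate, the plan does not say how the DSMB would learn of an expected SAE in time to meet.

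**What to change.** Reconcile sections 7.2, 7.4, 7.6, 8 and 9.4 into one rule that states which SAEs reach the monitors at occurrence and which trigger a DSMB meeting. Then:

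- Align the 7.2 row for expected or unrelated SAEs with that rule, for example by splitting it by relatedness, so that every SAE that triggers a meeting is notified in time for it.
- State whether unrelated SAEs trigger a meeting, since section 7.6 conflicts with sections 8 and 9.4. Splitting the row does not settle this.
- State how expectedness is judged, including whether the section 7.1 list is the reference and whether severity counts.
- Give the interval for the monitors in section 7.4, and use one name for the monitoring body throughout.

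The choice of trigger is for the sponsor and the board; the requirement is that the sections agree. The cost is protocol wording and a few more prompt notifications to monitors already appointed. Sample size, data collection and analysis are unaffected.
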